Other local radiotherapy is not permitted with the following exception. It is understood that there may be circumstances requiring local radiotherapy in which the investigator does not believe that the symptoms are a result of disease progression (e.g., impending fracture) and the radiation field does not encompass a target/non-target lesion. In such cases, the patient should have a tumor assessment of the lesion(s) before they receive radiotherapy. If a patient received radiation therapy and a target or non-target lesion was included in the field of radiation, the lesion(s) will become unevaluable for tumor response.

Further reasons for avoiding local radiotherapy include the difficulty in distinguishing new symptomatic pain or worsening of lytic bone lesions from disease progression. Time-to-Deterioration in Pain is a secondary endpoint of this study and Time-to-First-Skeletal-related-Event is an exploratory endpoint; palliative radiotherapy may alter these results. As such, palliative radiotherapy to bone in the absence of disease progression may be allowed after consultation with the Medical Monitor, however, such patients will be censored from the aforementioned

secondary and exploratory endpoints. Few clinical data are available about potential toxicities of radiation and treatment with inavolisib. Study treatment should be held ~24 hours prior to palliative radiotherapy and until any effects or sequelae have resolved to Grade \leq 1. Patients should not miss more than one cycle of study treatment due to radiation treatment and must meet eligibility requirements to continue *in the* study treatment (Section 4.1.1). Previous clinical experience also suggests that new bone pain is frequently a symptom of disease progression. Bone pain secondary to fulvestrant treatment may be treated with pain medications, nonsteroidal anti-inflammatory drugs (NSAIDs), or corticosteroids.

- Primary prophylactic use of hematopoietic growth factors (e.g., erythropoietins, granulocyte colony-stimulating factor [G-CSF], and *granulocyte-macrophage colony-stimulating factor* is not permitted, however, they may be used to treat treatment-emergent neutropenia or anemia as indicated by the current ASCO guidelines or as secondary prophylaxis if dose reduction or delay is not considered a reasonable alternative.

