A representative FFPE block (preferred) or approximately 20 (25 preferred) slides containing unstained, freshly cut, serial tumor tissue sections will be required for enrollment eligibility purposes. If fewer than 20 slides are available, the patient may still be eligible for the study following consultation with the Sponsor.

Tumor tissue should be of good quality based on total and viable tumor content. The submitted specimen should preferably be from the same block used for any local *PIK3CA* mutation testing, if preexisting local test results will be reported to the Sponsor to determine eligible *PIK3CA* mutation status, and accompanied by the associated local pathology report. Samples should contain a minimum of 500 viable tumor cells that preserve cellular context and tissue architecture regardless of needle gauge or retrieval method. Samples collected via resection, core-needle biopsy (three cores preferred, embedded in a single paraffin block), or excisional, incisional, punch or forceps biopsy types are acceptable. Fine-needle aspiration (defined as samples that do not preserve tissue architecture and yield cell suspension and/or smears), brushing, cell pellets from pleural effusion, and lavage samples are not acceptable. Tumor tissue from bone metastases is not acceptable. A detailed description of tissue quality requirements and procedures for collection, handling, and shipping of the samples will be provided in a separate laboratory manual.

- Any patient, except those enrolled in China, may provide optional consent to submit tumor tissue collected during treatment and/or at the time of disease progression (see [Appendix 1](#)).

Tissue submission guidelines for optional on-treatment and end-of-treatment biopsies should follow those for pre-treatment tumor biopsies, above. Please also refer to the laboratory manual.

Note: It is preferred that a target lesion (TL) not be biopsied while *in the* study treatment; however, if there is no other viable lesion and a TL is biopsied, it must be treated in the same manner as a TL that has been included in a field of radiation (Section [4.4.3](#)) and can no longer be eligible for tumor response. Such a TL must remain as a TL due to its inclusion at baseline and must subsequently be marked "Unable to Evaluate." As such, the Overall Assessments must also subsequently be "Unable to Evaluate" except in cases of PD or CR; PR and SD will no longer be possible for this patient.

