- Complete response (CR): Disappearance of all target lesions
- Any pathological lymph nodes (whether target or non-target) must have reduction in short axis to < 10 mm.
- Partial response (PR): At least a 30% decrease in the sum of diameters of target lesions, taking as reference the baseline sum of diameters
- Progressive disease (PD): At least a 20% increase in the sum of diameters of target lesions, taking as reference the smallest sum *in the* study (nadir), including baseline
- In addition to the relative increase of 20%, the sum must also demonstrate an absolute increase of at least 5 mm.

Appendix 11: Response Evaluation Criteria in Solid Tumors (RECIST): Modified Excerpt from Original Publication

- The appearance of one or more new lesions is also considered progression.
- Stable disease (SD): Neither sufficient shrinkage to qualify for PR nor sufficient increase to qualify for PD, taking as reference the smallest sum *in the* study

b. Special Notes on the Assessment of Target Lesions

Lymph Nodes. Lymph nodes identified as target lesions should always have the actual short axis measurement recorded (measured in the same anatomical plane as the baseline examination), even if the nodes regress to < 10 mm *in the* study. This means that when lymph nodes are included as target lesions, the sum of lesions may not be zero even if complete response criteria are met, since a normal lymph node is defined as having a short axis of < 10 mm.

Target Lesions That Become Too Small to Measure. During the study, all lesions (nodal and non-nodal) recorded at baseline should have their actual measurements recorded at each subsequent evaluation, even when very small (e.g., 2 mm). However, sometimes lesions or lymph nodes that are recorded as target lesions at baseline become so faint on CT scan that the radiologist may not feel comfortable assigning an exact measure and may report them as being too small to measure. When this occurs, it is important that a value be recorded on the CRF, as follows:

- If it is the opinion of the radiologist that the lesion has likely disappeared, the measurement should be recorded as 0 mm.

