Appendix 11: Response Evaluation Criteria in Solid Tumors (RECIST): Modified Excerpt from Original Publication

there is definitely a new lesion, then progression should be declared using the date of the initial scan.

Evaluation of Response

a. Timepoint Response (Overall Response)

It is assumed that at each protocol-specified timepoint, a response assessment occurs. [Table 1](#) provides a summary of the overall response status calculation at each timepoint for patients who have measurable disease at baseline.

When patients have non-measurable (*thus* non-target) disease only, [Table 2](#) is to be used.

Table 1 Timepoint Response: Patients with Target Lesions (with or without Non-Target Lesions)

Target Lesions	Non-Target Lesions	New Lesions	Overall Response
CR	CR	No	CR
CR	Non-CR/-non-PD	No	PR
CR	Not evaluated	No	PR
PR	Non-PD or not all evaluated	No	PR
SD	Non-PD or not all evaluated	No	SD
Not all evaluated	Non-PD	No	NE
PD	Any	Yes or no	PD
Any	PD	Yes or no	PD
Any	Any	Yes	PD

CR=complete response; NE=not evaluable; PD=progressive disease; PR=partial response; SD=stable disease.

Appendix 11: Response Evaluation Criteria in Solid Tumors (RECIST): Modified Excerpt from Original Publication

Table 2 Timepoint Response: Patients with Non-Target Lesions Only

Non-Target Lesions	New Lesions	Overall Response
CR	No	CR
Non-CR/non-PD	No	Non-CR/non-PD ^a
Not all evaluated	No	NE
Unequivocal PD	Yes or no	PD
Any	Yes	PD

CR=complete response; NE=not evaluable; PD=progressive disease.

^a “Non-CR/non-PD” is preferred over “stable disease” for non-target disease since stable disease is increasingly used as an endpoint for assessment of efficacy in some trials; thus, assigning “stable disease” when no lesions can be measured is not advised.

b. Missing Assessments and Not-Evaluable Designation

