When no imaging/measurement is done at all at a particular timepoint, the patient is not evaluable at that timepoint. If only a subset of lesion measurements are made at an assessment, usually the case is also considered not evaluable at that timepoint, unless a convincing argument can be made that the contribution of the individual missing lesion(s) would not change the assigned timepoint response. This would be most likely to happen in the case of PD. For example, if a patient had a baseline sum of 50 mm with three measured lesions and during the study only two lesions were assessed, but those gave a sum of 80 mm, the patient will have achieved PD status, regardless of the contribution of the missing lesion.

If one or more target lesions were not assessed either because the scan was not done or the scan could not be assessed because of poor image quality or obstructed view, the response for target lesions should be “unable to assess” since the patient is not evaluable. Similarly, if one or more non-target lesions are not assessed, the response for non-target lesions should be “unable to assess” except where there is clear progression. Overall response would be “unable to assess” if either the target response or the non-target response is “unable to assess” except where this is clear evidence of progression, as this equates with the case being not evaluable at that timepoint.

Appendix 11: Response Evaluation Criteria in Solid Tumors (RECIST): Modified Excerpt from Original Publication

Table 3 Best Overall Response When Confirmation Is Required

Overall Response at First Timepoint	Overall Response at Subsequent Timepoint	Best Overall Response
CR	CR	CR
CR	PR	SD, PD, or PR ^a
CR	SD	SD, provided minimum duration for SD was met; otherwise, PD
CR	PD	SD, provided minimum duration for SD was met; otherwise, PD
CR	NE	SD, provided minimum duration for SD was met; otherwise, NE
PR	CR	PR
PR	PR	PR
PR	SD	SD
PR	PD	SD, provided minimum duration for SD was met; otherwise, PD
PR	NE	SD, provided minimum duration for SD was met; otherwise, NE
NE	NE	NE

CR=complete response; NE=not evaluable; PD=progressive disease; PR=partial response; SD=stable disease.

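### Protocol Section 4.5.6 lets a patient with a biopsied target lesion marked as not evaluable be recorded as a complete response, which conflicts with the response rules in Appendix 11

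*Protocol*

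**What the plan says.** Protocol Section 4.5.6 prefers that target lesions are not biopsied on treatment, but allows it when no other viable lesion exists. For that case it sets a recording rule. The lesion "can no longer be eligible for tumor response". It stays on the target list: "Such a TL must remain as a TL due to its inclusion at baseline and must subsequently be marked" as unable to be evaluated. The overall assessment must then carry the same label, "except in cases of PD or CR; PR and SD will no longer be possible for this patient".

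Section 4.5.6 links this to radiotherapy by saying of the biopsied lesion that "it must be treated in the same manner as a TL that has been included in a field of radiation", citing Section 4.4.3. That section says of an irradiated target or non-target lesion only that "the lesion(s) will become unevaluable for tumor response". It states no exception for CR.

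Appendix 11 holds the general RECIST rules for the trial:

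- The target-lesion definition is "Complete response (CR): Disappearance of all target lesions".
- Table 1 gives an overall response of NE when target lesions are not all evaluated, non-target disease is not progressing and there is no new lesion.
- The text on missing assessments begins "If one or more target lesions were not assessed either because the scan was not done or the scan could not be assessed" and makes the target response unassessable. The overall response then follows, unless there is clear evidence of progression.

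The SAP takes response as determined by the investigator under RECIST v1.1. It has no rule for a target lesion that has become unevaluable.

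**The concern.** CR is the category that most depends on seeing every target lesion, yet Section 4.5.6 leaves CR open while closing PR and SD. A site following Section 4.5.6 could record CR at a visit that Appendix 11 would classify as NE.

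ORR, BOR and CBR all count CR. SAP Section 4.3 places them second, third and fourth in the fixed-sequence hierarchy of type I error-controlled secondary endpoints, after OS. In each, a patient who does not meet the criterion is a non-responder. The two protocol rules can therefore put the same patient on opposite sides of a formally tested endpoint, and the SAP does not say which rule governs. ORR status also decides who enters the descriptive analysis of duration of response.

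How the lesion was sampled matters too. Sections 4.5.6 and 4.5.11 accept resection and excisional biopsy, so a target lesion can vanish because it was removed rather than because it responded.

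**Working it through.** The plan gives no figure to reproduce. The check compares the two rules for one visit at which one target lesion is marked as not evaluable, non-target disease is not progressing and no new lesion is seen (except in the PD row).

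| Overall category | Section 4.5.6 | Appendix 11 | Agreement |
|---|---|---|---|
| PD | allowed | allowed when progression is clear | agree |
| PR | not possible | NE | agree |
| SD | not possible | NE | agree |
| CR | allowed | NE; disappearance of all target lesions not shown | conflict |

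Only the CR row differs.

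**Effect on the endpoints, for a patient with no earlier qualifying response**

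- BOR (SAP Section 4.3.1.3) needs a CR or PR, with no confirmation stated. One CR under the exception is enough.
- ORR (SAP Section 4.3.1.2) needs CR or PR on two consecutive occasions at least 4 weeks apart. One CR is not enough. Because PR is closed to this patient after the biopsy, the confirming visit must also be a CR under the exception.
- CBR (SAP Section 4.3.1.4) counts CR, PR and/or SD for at least 24 weeks. After the biopsy only the CR route remains, so CBR could be affected.
- PFS: progression can be recorded under both rules, so PFS events do not change.

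**Who could have no earlier response.** Section 4.5.11 schedules the optional on-treatment biopsy between Days 15 and 22 of Cycle 1. The first post-baseline tumor assessment is at 8 weeks. If a target lesion is biopsied in that window, every post-baseline assessment falls under the disputed rule.

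**Size per patient.** With about 320 patients randomized 1:1, each arm has 320/2 = 160. One patient classified differently moves that arm's rate by 1/160 = 0.00625, about 0.6 percentage points. The documents give no expected number of such patients.

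**The case against.** The best defence is that Section 4.5.6 can be read sensibly. Taking tissue from a lesion spoils its diameter, so percentage change, and with it PR and SD, is no longer reliable. Complete disappearance needs no diameter and can be seen on a scan. On this reading CR still requires the biopsied lesion to be gone. Appendix 11 never mentions on-study biopsy, its sentence on unassessed lesions names missing or poor scans, and it allows an exception where a convincing case shows that the missing lesion could not change the result.

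Part of this stands. Appendix 11 does not expressly prohibit CR after a biopsy; the conflict arises because Section 4.5.6 itself imposes the not-evaluable mark, which brings Table 1 and the CR definition into play. The defence does not remove the conflict, for three reasons. With that mark mandatory, disappearance of the lesion is never recorded. A resected or excised lesion is gone because of the procedure. And the allowance for a convincing case cannot support CR, because CR depends on every target lesion.

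The objection on size is stronger. An effect needs optional consent (not offered in China), no other viable lesion, an actual biopsy of a target lesion, and then a claimed CR. Protocol Section 1.3.2 mentions one CR among the 157 Phase I patients whose responses it describes, or one among the 33 + 13 + 15 = 61 in the arms that included palbociclib. Scaled to 320 patients, that is 320/157 ≈ 2 to 320/61 ≈ 5 CRs. If 5% to 10% of patients had a target lesion biopsied (an assumption; the documents give no figure), the expected number is about 2 × 0.05 = 0.1 to 5 × 0.10 = 0.5 in the whole trial. This is only a rough guide, since a lesion removed by the procedure could make a claimed CR more likely. The rule also applies to both arms of a double-blind trial, so no direction of bias is shown.

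**Conclusion.** The conflict is real. Section 4.5.6 leaves CR open for a patient whose biopsied target lesion it requires to be marked as not evaluable, and Appendix 11 does not support that classification. It is a minor point. Few patients are likely to be affected, possibly none, at about 0.6 percentage points of an arm's rate each, assuming about 160 patients per arm.

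A reader might infer more than the documents support:

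- That every such CR turns a non-responder into a responder. It does so at once only for BOR. ORR needs a second qualifying response at least 4 weeks later, and a patient with an earlier qualifying response is a responder under either rule.
- That the protocol allows CR with an irradiated target lesion. This is only an inference from the instruction to treat the two alike; Section 4.4.3 contains no CR exception.
- That the primary result is exposed. PFS events are unaffected.

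**What to change.** In Section 4.5.6, limit the exception to PD by deleting CR from it, and add CR to the categories that are no longer possible, so that the sentence rules out CR, PR and SD alike. Cross-refer to this wording from Section 4.4.3, so that irradiated target lesions are recorded in the same way and both sections agree with Appendix 11 Table 1.

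Add a matching data check that flags any overall CR recorded at or after a visit where a target lesion is marked as not evaluable. Because response is determined by the investigator, the check belongs on the recorded overall responses.

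The cost is a few words and one check. The downside is that a rare patient whose disease has truly disappeared may lose a claimed CR.

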4.5.7 Ophthalmologic Examinations

Patients will undergo ophthalmic examinations at baseline during the screening period, at Cycle 6 (± 2 weeks) during the study treatment period, at study treatment discontinuation, and based on any ocular disturbances. The ophthalmic examination should consist of a full ophthalmic exam with dilation and refraction with specific attention paid to lens examination and detailed documentation. In addition, patients will be asked if they have experienced any significant visual changes, pain, or sensitivity to light at each clinic visit. Any new eye-related symptoms including significant change in

vision, eye pain, or photophobia will be evaluated by an ophthalmologist. All clinically significant findings should be reported as Adverse Events.

4.5.8 Electrocardiograms

Triplicate 12-lead ECG recordings will be obtained at baseline to determine eligibility; otherwise, single 12-lead ECG recordings will be obtained at specified timepoints during study treatment, as outlined in the schedule of activities (see [Appendix 1](#)), and may be obtained at unscheduled timepoints as clinically indicated.

All ECG recordings must be performed using a standard high-quality, high-fidelity digital electrocardiograph machine equipped with computer-based interval measurements. Lead placement should be as consistent as possible. ECG recordings must be performed after the patient has been resting in a supine position for at least 10 minutes. All ECGs are to be obtained prior to other procedures scheduled at that same time (e.g., vital sign measurements, blood draws) and should not be obtained within 3 hours after any meal. Circumstances that may induce changes in heart rate, including environmental distractions (e.g., television, radio, conversation) should be avoided during the pre-ECG resting period and during ECG recording.

For safety monitoring purposes, the investigator must review, sign, and date all ECG tracings. Paper copies of ECG tracings will be kept as part of the patient's permanent study file at the site. Digital recordings will be stored at the site. The following should be recorded in the appropriate eCRF: heart rate, RR interval, QRS interval, PR duration, uncorrected QT interval, and QT interval corrected through use of Fridericia's formula based on the machine readings of the individual ECG tracings. Any morphologic waveform changes or other ECG abnormalities must be documented on the eCRF.

Clinically significant abnormalities observed during screening will be recorded on the General Medical History and Baseline Conditions eCRF. New or worsened clinically significant abnormalities observed during the Study Treatment period will be recorded on the Adverse Event eCRF.

4.5.9 Clinical Outcome Assessments

Patient-reported outcome data will be collected to more fully characterize the clinical profile of inavolisib in combination with palbociclib and fulvestrant compared with placebo plus palbociclib and fulvestrant in patients enrolled in the study. PRO data will be collected via electronic questionnaires at the clinic sites or patients' home using the following instruments: EORTC QLQ-C30, BR23, "worst pain" item from the BPI-SF, select items of the PRO-CTCAE, and the EQ-5D-5L. The questionnaires, translated into the local language as appropriate, will be distributed by the site staff or via secure web portal and completed in their entirety by the patient at baseline (Cycle 1, Day 1) and as noted in the schedule of activities (see [Appendix 1](#)).

In the event that after completion of the PROs at the start of a treatment cycle it is determined that the dose of palbociclib should be delayed, the Day 1 PROs will not be re-administered when the patient returns to the clinic following the delay. Additionally, the timing of subsequent PRO assessments (e.g., Day 15 during Cycles 2 and 3, and Day 1 of subsequent cycles after a delay) will be based on the actual Day 1 of the given cycle, when palbociclib was administered. For example, PROs will be completed at the *planned* Cycle 2, Day 1 visit prior to the actual office visit. In the event that the review of clinical laboratory results and adverse events (AEs) demonstrates that palbociclib should not be resumed at this visit (e.g., neutropenia), the actual Cycle 2, Day 1 visit will not occur until the patient is fit to resume palbociclib dosing. Frequently, this may require a 1-week delay. If appropriate, inavolisib and fulvestrant dosing may continue. PROs will not be repeated at the delayed Cycle 2, Day 1 visit when palbociclib dosing resumes. PROs will be administered at the new Cycle 2, Day 15, calculated from the resumption of palbociclib dosing.

4.5.9.1 Data Collection Methods for Clinical Outcome Assessments

Patient-reported outcome instruments will be self-administered at the clinic at specified timepoints during the study (see schedule of activities in [Appendix 1](#)). At the clinic, instruments will be administered before the patient receives any information on disease status, prior to the performance of study assessments, and prior to the administration of study treatment, unless otherwise specified. In cases where laboratory assessments (e.g., blood draws) are performed at a different location from the one providing treatment or where they are performed on a different day from study treatment administration, laboratory assessments can be completed before the completion of PROs as long as results have not been discussed with the patient.

Patient-reported outcome instruments, translated into the local language as appropriate, will be completed through use of an electronic device provided by the Sponsor or through a secured website. The device and the secured website will be pre-programmed to enable the appropriate instruments to be administered in the correct order at each specified timepoint. The electronic device/secured website and instructions for completing the instruments electronically will be provided by the site staff. In cases where the electronic device cannot be used (e.g., patient is unable to visit the site in person or elects MN visit), the instruments can be administered through a secured website. The data will be transmitted to a centralized database maintained by the electronic device vendor. The data will be available for access by appropriate study personnel.

During clinic visits and visits conducted by a mobile nurse ([Appendix 1](#)), PRO instruments should be administered as outlined below:

- Patients' health status should not be discussed prior to administration of the instruments.

- Sites must administer the official version of each instrument that is included on the electronic device, as provided by the Sponsor. Instruments must not be printed from the protocol and given to patients on paper.
- Sites should allow sufficient time for patients to complete the instruments, estimated to be 10–15 minutes at each visit specified in the schedule of activities (see [Appendix 1](#)).
- Sites should administer the instruments in a quiet area with minimal distractions and disruptions.
- Patients should be instructed to answer questions to the best of their ability; there are no right or wrong answers.
- Site staff should not interpret or explain questions, but may read questions verbatim upon request.
- Patients should not obtain advice or help from others (e.g., family members or friends) when completing the instruments.

During the post-treatment follow-up period, patients may be contacted by site staff or a mobile nurse with a request to complete the PRO instruments at home through a website if they are not able to visit the site. Patients should be given the following instructions for completing PRO instruments at home:

- Patients should complete the instruments in a quiet area with minimal distractions and disruptions.
- Patients should answer questions to the best of their ability; there are no right or wrong answers.
- Patients should not obtain advice or help from others (e.g., family members or friends) when completing the instruments.

